### Listing of Adverse Events

Listings present all Adverse Event data (raw, derived, and coded) for the SAF, ordered within patient by onset date and time and end date and time of the event.

### Serious Adverse Events

A listing presents all Adverse Event data (raw, derived, and coded, equivalent to the format for the AE listings) ordered within patient by onset date and time and end date and time of the event, for Serious AEs.

### Deaths

A listing presents all Adverse Event data (raw, derived, and coded, equivalent to the format for the AE listings) ordered within patient by onset date and time and end date and time of the events with outcome Death.

### Adverse Events that led to discontinuation of Study Treatment

A listing presents all Adverse Event data (raw, derived, and coded, equivalent to the format for the AE listings) ordered within patient by onset date and time and end date and time of the events that led to discontinuation of Study Treatment.

### 10.7.2 Clinical Laboratory Evaluation

Separate listings for hematology, chemistry, urinalysis, hemolysis panel and the special laboratory parameters present the raw values, normal ranges, investigators interpretation (for special laboratory parameters only) and, for all quantitative tests, the results converted to SI units for the SAF. Special laboratory data for adrenal insufficiency screening, early morning plasma cortisol and ACTH stimulation test are listed separately for the SAF.

Data for each parameter of a continuous nature are summarized, separately for hematology, chemistry and the special laboratory parameters, for the SAF. The change from baseline to each visit is calculated and summarized. Data for each parameter of a categorical nature is summarized descriptively using absolute counts (n) and percentages (%).

Clinically notable changes in laboratory values are summarized separately for hematology, chemistry and urinalysis using absolute counts (n) and percentages (%).

Results of the investigators interpretation of special laboratory parameters are presented as a shift table comparing each visit to Baseline for the SAF.

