Statistical Methods	Descriptive statistics (n, mean, standard deviation [SD], median, minimum, and maximum) will be provided for all continuous efficacy measures for actual values and changes from baseline of Study IEDAT-03-2018 at each time-point. For categorical variables, the number and percentage of patients in each category will be presented at each time-point. The analysis of long-term efficacy of EDS-EP is an exploratory objective of this extension study, and will be based on the results for the “Modified” International Cooperative Ataxia Rating Scale (mICARS), and the Clinical Global Impression of severity and change (CGI-S/C). The mean (SD) change from baseline at each time-point will be evaluated for the mICARS and the CGI-S. For the CGI-Change, the proportion [n(%)] of patients rated as improved, as well as those showing no change or worsening, at each time-point will be calculated. Additional analyses will be performed to determine the change in each of the efficacy measures compared to the baseline of the IEDAT-02-2015 study, comparing patients who were treated with EDS-EP throughout the double-blind and open-label treatment periods vs. those who received placebo for varying periods in Study IEDAT-02-2015, before being switched to the active treatment. As a secondary objective, similar descriptive analyses will be performed to evaluate the long-term effects of EDS-EP on health-related Quality of Life (QoL), as assessed by the EQ-5D-5L scale. Descriptive statistical analyses of changes from baseline will be performed for all safety parameters. Abnormal and clinically notable values will be identified and listed for each parameter, as appropriate.
Analysis Populations	The following analysis sets will be used:  1) Efficacy Population (EP) : All patients who enter study IEDAT-03, have a baseline efficacy assessment in study IEDAT-03, and who received at least one dose of study medication and had at least one post-baseline efficacy assessment of the primary efficacy variable in this extension study.  2) Safety Population (SP) : All subjects who receive a dose of study medication, and have at least one post-dose safety assessment will be included in the safety analyses.

**Schedule of Visits and Assessments: 1st year of open-label extension treatment (Visit 1 to Visit 13 to be replicated for the second year onwards)**

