#### *Baseline*

Final evaluations for the IEDAT-02-2015 trial will serve as baseline evaluations for patients continuing in the IEDAT-03-2018 study. The following "baseline" assessments for IEDAT-03-2018 will be done as part of the final Vist 15 evaluation in Study IEDAT-02-2015: physical/neurological examination; 12-lead

standard ECG; laboratory evaluations [including hematology, clinical chemistry, urinalysis, serum pregnancy test (women of childbearing potential); special laboratory tests: HbA1c, CD4+ lymphocytes count and CRP]; assessment of physical development, sexual maturation, and the effect of treatment with dexamethasone on these aspects (Tanner scale); ICARS; CGI-S; CGI-S; VABS: EQ-5D-5L; C-SSRS; BMD; review of AEs and concomitant medications.

After providing consent/assent, as described in [Section 11.1](#), each patient will undergo evaluation of the eligibility criteria at the baseline visit, and if eligible, will proceed with the EDS-EP infusion. Demographic information will be rolled over from the IEDAT-02-2015 eCRF and rechecked by the Investigators for consistency, as well as medical history.

Before the EDS-EP infusion, all patients will undergo vital signs evaluation, hemolysis panel (on the diverted blood sample, see [Section 11.5](#)) and assessment of prior and concomitant medication and AEs. Women of childbearing potential must undergo a urine pregnancy test. .

CCI  
[Redacted text block]

Study treatment administration by IV infusion will be performed within 30 min after the EDS process has been completed.

CCI  
[Redacted text block]

After completion of the IV infusion of the study treatment the following assessments will be performed on Day 0 (Baseline/Visit 1): Vital signs, physical examination (1-2 hr after infusion), assessment of AEs, and assessment of concomitant medications.

*Months 1-5 and 7- 11*

Before the EDS-EP infusion, patients must undergo to laboratory tests: the diverted blood sample (see [Section 11.5](#)) will be collected for measurement of serum creatinine and routine tests. Women of childbearing potential must undergo a pregnancy urine test.

A C-SSRS assessment, will be performed at each of these visits, as well as a vital signs assessment. In addition, a hemolysis panel on diverted blood sample (see [Section 11.5](#)) will be done at the Month 4 and Month 8 visits.

All patients should undergo assessment of prior and concomitant medication and AEs.

CCI  
[Redacted text block]

CCI  
[Redacted]

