11.4.3 Months 1-5 (Visits 2-6) and 7- 11 (Visits 8-12)

At Months 1- 5 and 7- 11, the following assessments will be performed:

- a) Laboratory tests, on the diverted blood sample (see Section 11.5): serum creatinine
- b) Routine laboratory tests, on the diverted blood sample (see Section 11.5):
  - hematology
  - clinical chemistry
  - urinalysis
- c) Hemolysis panel (including urinalysis), on the diverted blood sample (see Section 11.5): only at Month 4 and 8
- d) Urine pregnancy test will be performed before every infusion (for women of childbearing potential)
- e) C-SSRS
- f) Assessment of prior and concomitant medication
- g) Assessment of AEs - reported by the patient or observed by the Investigator
- h) 1 mL blood collected, after blood diversion (see Section 11.5), for aerobic culture
- i) Autologous blood collection for EDS processing
- j) Addition of the assigned study medication (DSP) to the EDS process
- k) Upon completion of the EDS process, fill the satellite sample bag with CCI [REDACTED] if no other samples but the ones for sterility culture test will be collected).
- l) Study treatment administration by IV infusion, within 30 min after the EDS process has been completed.
- m) CCI [REDACTED]  
[REDACTED]  
[REDACTED]  
[REDACTED]  
[REDACTED]  
[REDACTED]  
[REDACTED]  
[REDACTED]

After completion of the IV infusion of the study treatment the following assessments will be performed:

- n) Physical examination and vital signs (body weight and height, calculation of BMI, temperature - oral or tympanic, according to the specific medical practice of the Center - pulse, systolic and diastolic BP, and respiratory rate) 1-2 hr after the end of infusion
- o) Assessment of AEs and concomitant medications

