### 16.2.5 *Safety Evaluations*

All patients in the Safety Population will be included in the safety analyses. All adverse events will be listed and summarized by body system and preferred term. The incidence of AEs (%) and their intensity and relatedness to the study drug, as assessed by the Investigator, will be reported. Serious adverse events (SAEs) and events which are newly occurring or worsening after administration of the study medication will be summarized. In addition, adverse events that result in death or discontinuation (ADO) of the study medication will be listed separately.

Other safety parameters such as vital signs, standard laboratory parameters, ECGs, physical/neurological examination findings, and special laboratory parameters will be listed and summarized accordingly. Abnormal and clinically notable values will be identified and listed for each parameter, as appropriate.

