### 3.4 Efficacy and Safety Variables

#### Primary Endpoint

*The primary objective is to monitor and evaluate the long-term safety and tolerability of EDS-EP in AT patients. This will be done based on the occurrence of Treatment-Emergent Adverse Events (TEAEs), including Serious AEs and discontinuations due to AEs, and changes in vital signs, laboratory parameters, ECGs and physical/neurological examination findings.*

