| Listing 16.2.7-1.3   | Listing of Serious Adverse Events with Outcome Death                     | SAF               | R |
| Listing 16.2.7-1.4   | Listing of Adverse Events that led to Discontinuation of Study Treatment | SAF               | R |
| Clinical Laboratory Evaluation                      |  |                   |   |
| Listing 16.2.8-1.1   | Listing of Hematology Data   | SAF               | U |
| Listing 16.2.8-1.2   | Listing of Clinical Chemistry Data                                       | SAF               | R |
| Listing 16.2.8-1.3   | Listing of Urinalysis Data   | SAF               | U |
| Listing 16.2.8-1.4   | Listing of Special Laboratory Data                                       | SAF               | R |
| Listing 16.2.8-1.5   | Listing of Early Morning Plasma Cortisol                                 | SAF               | U |
| Listing 16.2.8-1.6   | Listing of ACTH Stimulation Test   | SAF               | U |
| Listing 16.2.8-1.7   | Listing of Adrenal Insufficiency Screening                               | SAF               | U |
| Listing 16.2.8-1.8   | Listing of Pregnancy Test Data   | SAF               | U |
| EDS-EP Infusion                                     |  |                   |   |
| Listing 16.2.9-1.1   | EDS-EP Infusion – EryDex system (EDS) process before Infusion            | SAF               | U |

|                      |  |     |   |
|----------------------|--|-----|---|
| Listing 16.2.9-1.2.1 | EDS-EP Infusion – Staining Test on EDS-End Product                 | SAF | U |
| Listing 16.2.9-1.2.2 | EDS-EP Infusion – Pre-infusion Aerobic Blood Culture               | SAF | U |
| Listing 16.2.9-1.3.1 | EDS-EP Infusion – 14-Day Sterility Test Sampling                   | SAF | U |
| Listing 16.2.9-1.3.2 | EDS-EP Infusion – RBC Osmotic Resistance                           | SAF | U |
| Listing 16.2.9-1.4   | EDS-EP Infusion – EryDex system End Product before Infusion        | SAF | U |
| Listing 16.2.9-1.5   | Listing of 14-Day Sterility Test Positive Staining Test            | SAF | U |
| Listing 16.2.9-1.6.1 | Listing of Positive post-Release Sterility Test                    | SAF | U |
| Listing 16.2.9-1.6.2 | Listing of Positive Post-Release Sterility Test – Retention Sample | SAF | U |
| Listing 16.2.9-2.1.1 | EDS Process - Encapsulation Procedure Checklist – Part 1           | SAF | U |
| Listing 16.2.9-2.1.2 | EDS Process - Encapsulation Procedure Checklist – Part 2           | SAF | U |

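### The hemolysis panel is a scheduled safety assessment, but the SAP plans no summary under its own name and omits its promised listing from the output index

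*SAP*

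**What the plan says.** **Collection.** Protocol 11.2 requires the panel at the baseline visit: "Before the EDS-EP infusion, all patients will undergo vital signs evaluation, hemolysis panel". For the monthly visits it adds: "In addition, a hemolysis panel on diverted blood sample", at Months 4 and 8. Protocol 11.4.3 confirms the timing as "only at Month 4 and 8". The schedule table and Protocol 11.4.5 add a draw at the safety follow-up visit, about 60 days after the last infusion. The first-year schedule is repeated in later years.

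**Required analysis.** The protocol synopsis states: "Descriptive statistical analyses of changes from baseline will be performed for all safety parameters". Protocol 16.2.5 says: "Other safety parameters such as vital signs, standard laboratory parameters, ECGs, physical/neurological examination findings, and special laboratory parameters will be listed and summarized accordingly". The primary endpoint in SAP 3.4 includes "changes in vital signs, laboratory parameters, ECGs and physical/neurological examination findings". SAP 8.3 says that all safety data receive descriptive summaries.

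**Planned output.** SAP 10.7.2 gives the hemolysis panel its own place among the laboratory listings. The next paragraph sets the scope of the continuous summaries: "Data for each parameter of a continuous nature are summarized, separately for hematology, chemistry and the special laboratory parameters, for the SAF". Counts of clinically notable changes are limited to hematology, chemistry and urinalysis. The shift table is limited to the special laboratory parameters.

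**The concern.** The product is the patient's own red cells, processed, loaded and reinfused monthly, in some patients for years. A scheduled hemolysis panel is an obvious place to look for slow drift. The protocol asks for change from baseline on all safety parameters and the panel has a pre-infusion baseline, so the analysis is both required and possible. A programmer who follows SAP 10.7.2 and the Section 12 index as written would produce no table for the panel and, going by the index, no listing either.

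Raw values would be hard to read without a summary. In the pharmacokinetic study described in Protocol 7.1.3.2, free hemoglobin was above normal before infusion in 4 of 9 and 6 of 9 subjects, possibly because of the blood-drawing technique. Against such background noise, by-visit change from the patient's own baseline tells more than individual values. SAP Section 9 also says that analyses of this study will support a New Drug Application.

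**Working it through.** The plan states no figure to reproduce. The check sets the passages side by side and then sizes the gap.

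**1. Is the panel covered under another laboratory heading?** The special laboratory tests are HbA1c, CD4+ count and CRP (note b of the schedule), with cortisol and ACTH testing handled as part of the special evaluations. The panel is not among them. SAP 10.7.2 lists it separately from hematology, chemistry and urinalysis. The schedule gives it its own row, and at Months 4 and 8 it is drawn in addition to the routine tests. On Day 0 it is drawn although no routine tests are scheduled.

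**2. Is there an output for it in SAP Section 12?**

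| Index | Entries | For the hemolysis panel |
|---|---|---|
| 12.1 laboratory tables (14.3.2-1.1 to 1.4, 2.1 to 2.3, 3.1) | 4 + 3 + 1 = 8 | 0 |
| 12.3 laboratory listings (16.2.8-1.1 to 1.8) | 8 | 0 |

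The index includes a "Listing of Special Laboratory Data", but by step 1 that does not take in the panel. No figure covers it.

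**3. Is the omission declared?** SAP 3.6 records the change to the safety set, a renamed schedule column, the added treatment groups and subgroups, the rescored scale, continuous exposure and the 12-month adverse event periods. It does not mention the hemolysis panel.

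**4. What do the routine summaries already cover?** Protocol Table 3 includes hemoglobin, hematocrit, red cell count, LDH, total bilirubin, and urine hemoglobin, bilirubin and urobilinogen. These are drawn at Visits 2 to 13 and at safety follow-up. Hematology and chemistry get by-visit values and change from baseline, urinalysis has a summary table, and all three get clinically notable counts. Plasma free hemoglobin, measured in the earlier pharmacokinetic study, is not in Table 3. Whether it belongs to the panel is not stated.

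**5. How many results are affected?** Inputs: at most 150 patients (Protocol 16.2.1); panels at Visit 1, Month 4 and Month 8; none in the Month 12 (Visit 13) column. Full retention is assumed, so these are ceilings per panel parameter.

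- Year 1: 150 × 3 = 450, of which 150 are baseline and 150 × 2 = 300 are on treatment.
- A later year, if only Months 4 and 8 recur: 150 × 2 = 300.
- A later year, if the Visit 1 draw also recurs: 150 × 3 = 450.
- Safety follow-up: one further result per patient who returns, at most 150 over the whole study.

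**The case against.** The strongest reply is that hemolysis is not left unexamined. Routine markers are measured more often than the panel and are summarised. The account of the earlier pharmacokinetic study itself used urine hemoglobin, bilirubin and urobilinogen to look for hemoglobinuria. This stands, and it limits the point. A reader might infer that the primary safety objective cannot be answered for hemolysis, or that no panel result reaches any summary. The documents do not support either. The panel is described only as including urinalysis, its analytes are not itemised in the available text, and the SAP's laboratory parameter table is incomplete there. Some panel components may therefore be reported under routine headings.

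A second reply is that SAP 8.3, and the sentence in 10.7.2 on categorical parameters, are general enough to cover the panel. Protocol 16.2.5 gives only examples and does not name it, and neither does the list of safety assessments in Protocol Section 13. This makes an oversight more likely than a decision not to analyse. It does not remove the gap, because no table carries out the general statement and the listing that 10.7.2 does promise is absent from 12.3.

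A reader might also take the panel to be the only safety test specific to processed red cells. It is not: sterility results and process failures are summarised (SAP 10.7.4 and 10.7.5), and red cell osmotic resistance has a listing. Nor do the documents report a hemolysis signal. Protocol 7.1.3 reports no toxicity related to processed red cells, and 7.1.3.3 reports no consistent pattern on an earlier hemolysis panel.

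**Conclusion.** The point holds in bounded form. A scheduled safety assessment with a usable pre-infusion baseline has no planned summary under its own name, and its listing is promised in SAP 10.7.2 but missing from 12.3. This conflicts with the protocol synopsis and SAP 8.3 and is not declared in SAP 3.6.

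The loss is confined to analytes measured only in the panel and to the panel's own baseline and visits. Its ceiling is about 450 results per parameter in year 1, baseline included, and 300 to 450 in a later year. It would be wrong to read 450 as a fixed yearly number: it assumes that all 150 patients enter and stay, and in later years that the Visit 1 draw is repeated, which the Month 12 column does not show. How many analytes are affected cannot be determined from the available text. The omission should be corrected before the outputs are produced, but it does not undermine the safety analysis as a whole.

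**What to change.** - In SAP 10.7.2, add the hemolysis panel to the parameters summarised. For the Safety Analysis Set, give the value and the change from the Day 0 pre-infusion baseline at each scheduled panel visit and at safety follow-up.
- Add counts outside the local normal range. The normal ranges are already needed for the listing. This differs from what hematology receives, which is counts against the clinically notable limits.
- Name the panel analytes that are not already reported under routine laboratory tests, so that the table is defined and does not duplicate others.
- Add the table to SAP 12.1 and the missing listing to 12.3.

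If listing only is what is intended, SAP 3.6 should say so and give the reason, and the listing must still be added to 12.3.

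The cost is one extra table, one extra listing and a short statement of the panel's content. No new data are collected.

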	
CCI
 
█
 

• After completion of the IV infusion of the study treatment the following assessments will be performed:

○ Physical examination and vital signs 1-2 hr after infusion;

○ Assessment of concomitant medications;

○ Assessment of AEs.

 
The schedule of visits and assessments for the first 12 months - as described above- will be replicated for the second year onwards, if patients continue treatment for more than 12 months.
 
Safety Follow-up Visit
 
All patients who discontinue will be required to return for a Safety Follow-up Visit approximately 60 days (<math>\pm 7</math> days) after their last infusion. At this visit, plasma cortisol, pregnancy status (for women of childbearing potential), vital signs will be assessed, as well as the occurrence of any AEs or Serious AEs (SAEs) reported by the patient/caregiver or observed by the Investigator since the previous visit.

Investigational Medicinal Product(s): dose, mode of administration, and dosing schedule
	
The study treatment consists of a CCI dexamethasone sodium phosphate (DSP) administered via ex vivo encapsulation into autologous erythrocytes (EDS) that are infused into the patient with AT. The dose of EDS-EP has been selected to allow collection of long-term safety data on a high dose. However, if this dose is associated with significant tolerability issues that do not resolve, then the patient should be discontinued from the study.
 
Autologous whole blood CCI to be used for the EDS process will be collected according to the instructions provided in Section 11.5. Details of these procedures are described in a separate document entitled "Study Procedures on Sterility Testing for Study IEDAT-03-2018 (OLE-IEDAT)", which will be provided to each site (see Appendix 9). The study medication will be prepared with a CCI
 
Study treatment will be administered by monthly IV infusion.
 
CCI

Planned Treatment Duration per Patient	The open-label treatment period is planned for 12 months, but may be extended further and continue until patients eventually withdraw consent or the Investigator decides to discontinue treatment based on a risk/benefit assessment.

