#### Safety Results

The safety population included all 22 patients. Overall, 15 (68.2%) of patients experienced a total of 29 TEAEs, most of which were rated as mild (~60% of subjects) and not related to the study medication (> 90% of patients), with the exception of 1 patient with a mild hypercholesterolemia. Two SAEs were reported during the study, including one case of severe pneumonia and a second patient with bronchopneumonia, and bronchiectasis and bleeding; both patients required hospitalisation. Both cases were considered unrelated to study medication and resolved with treatment.

Two patients had a > 20% decrease in CD4+ lymphocytes count during the study period which resulted in premature discontinuation, and were considered related to study medication.

There were no clinically meaningful changes in mean values for routine laboratory parameters with EDS-EP treatment, except for serum iron, which showed a > 20% mean decrease from baseline value, with 8 patients having newly occurring abnormal (low) values at the final visit (one reported as a TEAE). For the special laboratory parameters, no clinically meaningful changes were observed, except for urinary cortisol, which showed an approximately 30% decrease from baseline to the final visit (statistically significant,  $p=0.016$ ). Although this could indicate an effect of EDS-EP on the hypothalamo-pituitary-adrenal axis, a comparison of blood and urinary cortisol levels versus dose did not indicate any relationship. No clinically significant changes with EDS-EP treatment were observed for vital signs, ECGs, or physical examination findings.

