### 13.5 Special Laboratory Evaluations

Measurement of selected “special” laboratory parameters has been included in the study to evaluate potential effects of dexamethasone (EDS-EP) treatment (for details on aseptic procedure for blood withdrawal and on blood diversion see “Study Procedures on Sterility Testing for Study IEDAT-03-2018 (OLE-IEDAT)”; [Appendix 9](#)). The following special laboratory parameters will be assessed in the study:

- Blood glycosylated hemoglobin (HbA1c, %), CD4+ lymphocytes and C-reactive protein (CRP)– to be performed at Months 6 and 12.
- Screening for adrenal insufficiency will be performed in all patients, regardless of weight, via early morning (before 8:00 AM) plasma cortisol testing at the following times: (1) when patients are symptomatic, and (2) when patients are at most risk for adrenal insufficiency and adrenal crisis, such as following discontinuation or interruptions of dexamethasone dosing (i.e., loading failures and following discontinuation of the study drug). If the 8:00 AM cortisol level is below 3-5 µg/dL (depending on assay) regardless of symptoms, or the patient exhibits signs or symptoms of adrenal insufficiency ([Appendix 12](#)) and has a cortisol <10 µg/dL, the patient will receive a high dose ACTH stimulation test, regardless of weight, within 24 hours. If the ACTH stimulation test is normal, the patient can continue dosing with EDS-EP, after the effects of the ACTH have dissipated (e.g., 30 days after ACTH administered). If the patient fails the ACTH stimulation test they will be discontinued from the study and referred to a pediatric endocrinologist, with a recommendation to prescribe stress dose steroids.

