**Table 2: Study Visits**

| Scheduled Visit        | Scheduled Visit Label | Scheduled Study Day         | Visit Window                   |
|------------------------|-----------------------|-----------------------------|--------------------------------|
| Visit 0                | Screening             | -30 - -1                    | Study day $\leq$ -1            |
| Visit 1                | Baseline              | 0                           | Study day = 0                  |
| Visit 2                | Month 1               | 28                          | Study day in [21 – 38]         |
| Visit 3                | Month 2               | 56                          | Visit 2 + [21 – 38] days       |
| Visit 4                | Month 3               | 84                          | Visit 3 + [21 – 38] days       |
| ...                    | ...                   | ...                         | ...                            |
| Visit x                | Month x-1             | 28(x-1)                     | Visit x-1 + [21 – 38] days     |
| Safety follow-up visit | Safety FU             | 60 days after last infusion | Last Infusion + [53 - 67] days |

The visit schedule of the first 12 months is repeated for subsequent visits.

Unscheduled Visits are labelled as "Unscheduled Visit y" with y in (1, 2, 3,). Data from unscheduled visits are presented in listings.

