## 8. Analysis Methods

### 8.1 General Methods

For continuous variables, the mean, standard deviation (SD), minimum, median and maximum as well as 1st and 3rd quartile (Q1, Q3) are presented, together with the total number of observations and the number of non-missing values. Unless otherwise specified minimum and maximum values are reported to the same number of decimal places as the recorded measurements, mean, median, 1st and 3rd quartile are reported to one more decimal place and standard deviation one additional decimal place more than the mean.

For categorical variables, absolute and relative frequencies are reported. Relative frequencies are based on all observations and reported as a percentage to one decimal place. Unless otherwise specified percentages are based on the number of patients with data and are not calculated for missing categories.

Adverse events, medical histories and concomitant medications are reported on a patient basis, i.e. if a patient reported several events coded to the same coding term the patient is counted only once at the respective level of display. The percentages are calculated using the number of patients in the population Analysis Set as the denominator.

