##### 8.2.1.2 Handling of Dropouts or Missing Data

Dropouts are not replaced.

Missing data are handled as described in section 7.

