#### **10.7.10 Bone Mineral Density**

All recorded BMD data are included in a listing for the SAF.

BMD z-scores, including change from baseline, are summarized at each scheduled visit. Results of the investigator's interpretation are presented as a shift table comparing each visit to Baseline for the SAF.

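### Later by-visit summaries of CD4+, HbA1c and BMD Z-score describe only patients still measured, and no last-value or worst-value summary shows how far the patients who left had changed

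*SAP*

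**What the plan says.** Change in laboratory parameters is part of the primary safety endpoint (Protocol 7.3, Primary Endpoint; SAP 3.4). SAP 10.7.2 gives the method for continuous laboratory parameters, including the special tests CD4+ and HbA1c: "The change from baseline to each visit is calculated and summarized". SAP 10.7.10 does the same for bone density: "BMD z-scores, including change from baseline, are summarized at each scheduled visit". Both sections add a shift table of the investigator's interpretation, again visit by visit against baseline.

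On who enters each row, SAP 8.1 says for percentages: "Unless otherwise specified percentages are based on the number of patients with data and are not calculated for missing categories". For unscheduled measurements, SAP 7.1 says: "Data from unscheduled visits are presented in listings". On dropouts, SAP 8.2.1.2 says only: "Missing data are handled as described in section 7".

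Protocol 13.5 schedules HbA1c and CD4+ together with "C-reactive protein (CRP)– to be performed at Months 6 and 12", and Protocol 13.8 puts BMD at the same two visits. The schedule repeats each year.

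On leaving treatment, the Protocol Synopsis says that "if this dose is associated with significant tolerability issues that do not resolve, then the patient should be discontinued from the study". The pilot study's safety results (Protocol 7.1.3.1) report: "Two patients had a > 20% decrease in CD4+ lymphocytes count during the study period which resulted in premature discontinuation". Those falls were judged related to study medication.

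**The concern.** A patient who leaves because of a steroid effect contributes to the visit at which the effect was measured and to no later row. If leaving is linked to the measured change, the later rows describe a progressively more tolerant group. Treatment is open-ended, so those rows are the ones a reader will use to judge long-term effects on CD4+, glycaemia and bone. A flat mean at Month 24 or 36 could reflect no drug effect or the departure of affected patients, and the planned tables cannot separate the two.

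CD4+, HbA1c and BMD are the most exposed. They are scheduled only every six months, and the safety follow-up visit does not name them. They also lack the measurement-based summaries that other safety data receive: vital signs have any-time and most-extreme summaries (SAP 10.7.6), and hematology, chemistry and urinalysis have clinically notable counts (SAP 10.7.2).

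**Working it through.** **1. Is there a rule for missing post-baseline values?** SAP Section 7, to which 8.2.1.2 refers, imputes incomplete event dates (7.2.2), replaces a missing baseline by the screening value (7.1) and sets incomplete scale totals to missing (7.4.7). In the text available it has nothing for a missing post-baseline laboratory or BMD value. Table 2 has no early-termination visit. The by-visit rows are therefore observed-case.

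**2. What happens at discontinuation?** The passages do not agree.
- Protocol 16.2.6, on dropouts, asks for the full Month 12 evaluations when a patient leaves before Month 12. Those include CD4+, HbA1c and BMD.
- Protocol 9.3, 11.4.5 and 15.2 mention only the safety follow-up visit.
- SAP 7.1 analyses data by nominal visit label. An exit measurement could therefore be pooled with true Month 12 data or, if recorded as unscheduled, only listed.
- The dropout passage covers only departures before Month 12, so it gives no rule for year two onward.

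**3. Size, simple arithmetic.** The plan has no figure to reproduce: the study is descriptive, with no sample size calculation. The one input from the documents is the pilot share, 2/22 = 9.1% (exact 95% CI 1.1% to 29.2%). The mean changes are assumptions. Let L be the mean change in the 2 who leave and R that in the 20 who stay.

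All-patient mean = (2L + 20R)/22. The later observed mean is R. Gap = R minus the all-patient mean.

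| L | R | All-patient mean | Observed later mean | Gap (points) |
|---|---|---|---|---|
| -20% | -5% | (-40 - 100)/22 = -6.4% | -5.0% | 1.4 |
| -30% | -5% | (-60 - 100)/22 = -7.3% | -5.0% | 2.3 |
| -40% | -5% | (-80 - 100)/22 = -8.2% | -5.0% | 3.2 |
| -20% | 0% | -40/22 = -1.8% | 0% | 1.8 |
| -40% | 0% | -80/22 = -3.6% | 0% | 3.6 |

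With R = 0, varying the share who leave from 1/22 (L = -20%) to 30% (L = -40%) gives gaps from 0.9 to 12 points.

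**4. Size, simulation.** Assume that percent change in CD4+ at Months 6 and 12 is normal with mean -5 and SD 20, with correlation 0.7. A fraction p of patients whose Month 6 fall exceeds 20% then leaves.

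| p | True Month 12 mean | Observed Month 12 mean | Mean at last on-treatment value | Fall above 20% at any time |
|---|---|---|---|---|
| 0.25 | -5.0 | -3.9 | -5.4 | 32.0% |
| 0.5 | -5.0 | -2.6 | -5.9 | 32.0% |
| 1 | -5.0 | +0.5 | -6.8 | 32.0% |

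The Month 6 mean stays at -5.0 throughout, so only the row after departure is affected. The last-value mean errs in the adverse direction, but by less (0.4 to 1.8 points, against 1.1 to 5.4 for the observed mean). The any-time count does not depend on p. With mean 0 and SD 15, the observed mean is too favourable by 0.4 to 1.9 points and the any-time share stays at 14.1%.

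**The case against.** The strongest reply is that the primary safety result does not rest on these rows. It rests first on treatment-emergent and serious adverse events and on discontinuations due to adverse events. These are counted with the whole analysis set as denominator (SAP 8.1, 10.7.1). The events of special interest name low CD4 count, low bone mineral density, osteopenia, osteoporosis and hyperglycemia (SAP 7.4.8), and events leading to discontinuation have a table and a listing. A reader might infer that the primary safety result loses its worst-affected patients. The documents do not support that. What remains is narrower: a laboratory change enters these tables only if the investigator reports it as an adverse event, the special-interest list depends on manual review, and neither shows how large the change was.

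A reader might also infer that patients with these effects are withdrawn by rule. They are not. The documents set no CD4+, HbA1c or BMD threshold for withdrawal; the only laboratory-triggered withdrawal stated is a failed ACTH stimulation test (Protocol 13.5). The rest is intolerance or the investigator's judgement.

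Nor does the point extend to all laboratory tests. Routine tests are monthly and have clinically notable counts.

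The pilot's 9.1% may not carry over, because the extension requires prior tolerance and excludes patients with moderate or severe steroid side effects. This stands, though patients who were on placebo throughout ATTeST start active treatment here. Finally, the SAP reports the number of non-missing values and visit attendance, so shrinking rows will be visible. That shows how many patients are missing, not how they had changed.

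**Conclusion.** The point holds for the later by-visit means and shift tables of CD4+, HbA1c and BMD Z-score. They are observed-case, discontinuation for intolerance makes the missingness plausibly informative, and no planned summary keeps the size of the change in patients who left. The value recorded at a scheduled visit before departure still counts in its own row.

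The size is not known. Under the pilot share and the assumed changes (-20% to -40% in those who leave, -5% in the rest), the gap is about 1.4 to 3.2 percentage points. A mean that turns positive despite a true fall appears only under the extreme assumption that every patient with a fall above 20% leaves. These figures concern CD4+; the documents offer no comparable precedent for HbA1c or BMD, so for those the argument is structural.

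One limit: SAP Appendix 13.1 and the start of the SAP laboratory section are not in the text available. However, SAP 10.7.2 and the table list confine clinically notable counts to hematology, chemistry and urinalysis. The matter is worth correcting, but it does not undermine the safety analysis as a whole.

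**What to change.** For CD4+, HbA1c and BMD Z-score only, extend SAP 10.7.2 and 10.7.10:

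- In Tables 14.3.2-1.3 and 14.3.3-6.1, add change from baseline to (a) the last on-treatment value and (b) the worst post-baseline value: lowest CD4+, highest HbA1c, lowest BMD Z-score. Add the corresponding shifts to Tables 14.3.2-3.1 and 14.3.3-6.2.
- Base both on all safety-set patients with a baseline and any post-baseline value, including values at discontinuation and at unscheduled visits. Define on-treatment in SAP 7.1, and note there the exception to the listings-only rule for unscheduled data.
- Reconcile the dropout passage in Protocol 16.2.6 with Protocol 9.3, 11.4.5 and 15.2 and with SAP Table 2. Report exit measurements under a separate early-termination label so that they are not pooled with true Month 12 data.

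Restricting this to three measures is deliberate. Many routine analytes can be abnormal in either direction, so a worst value would need a direction set for each.

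The cost is SAP wording and a few rows from data already collected, with a possibly less favourable figure. A worst value becomes more extreme as measurements accumulate, so it should be read beside follow-up duration and not compared directly between ATTeST groups followed for different times.
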